7.6 Medications

Missing and partial dates in medication start or stop date will be handled as shown in the table below.

Partial Date in start/stop date	Action Taken
Entire start date is missing	The procedure date will be used for the start date.
The month and the day of the month are missing but the year is available in start date	January 1 st will be used for the month and day for start date.
Day is missing, but the month and year are available in start date	The 1 st will be used as the start day.
Entire stop date is missing for discontinued medication	The start date will be used for the stop date.

Partial Date in start/stop date	Action Taken
The month and the day of the month are missing but the year is available in stop date	January 1 st will be used for the month and day for stop date. However, if the imputed stop date falls before the start date, then the start date will be used for the stop date.
Day is missing, but the month and year are available in stop date	The 1 st will be used as the stop day. However, if the imputed stop date falls before the start date, then the start date will be used for the stop date.

The following defined timeframe in medications.

Prior to implant: medication started prior to implant.

Post-implant: medication started and not stopped prior to implant OR medication started within 7 days post-implant.

14-day follow-up: medication started anytime (including prior to implant) up to 14 days and not stopped before 14 days post-implant.

45-day follow-up: medication started anytime (including prior to implant) up to 45 days and not stopped before 45 days post-implant.

3-month follow-up: medication started anytime (including prior to implant) up to 90 days and not stopped before 90 days post-implant.

1-year follow-up: medication started anytime (including prior to implant) up to 365 days and not stopped before 365 days post-implant.

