10.4. Baseline Assessments

The following pre-procedure data should be collected within 30 days prior to the index procedure for all patients but will follow local standard of care practice. If mRS is not standard of care prior to the Index Procedure, it is to be collected by study personnel per Section 10.9.1. Baseline assessments performed per Standard of Care outside of the 30-day window can be used and will not be a protocol deviation if no data within 30 days are available. Assessments indicated with an '*' are expected to be collected prior to implant.

- Confirmation of eligibility criteria
- Clinical assessments
 - Demographics, including age at time of consent, race, ethnicity, and sex
 - Medical, cardiac, and neurological history including cardiovascular diseases, AF type (paroxysmal/persistent/permanent) and time since AF diagnosis; prior history of ischemic stroke, hemorrhagic stroke and/or TIA; previous cardiac procedures; history of bleeding and location; and NSAID use
 - HAS-BLED, and CHA₂DS₂-VASc scores*
 - Physical assessment includes height and weight*
 - Current medication regimen review for the use of antiplatelet, aspirin, and anticoagulant medications
 - Modified Rankin Scale (mRS)*
 - Pregnancy test for Women Of Childbearing Potential, who are pregnant or plans to become pregnant during the time of the study (method of assessment per investigator discretion) *
- Imaging assessments
 - Pre-procedural imaging (TEE / CT) is recommended per the IFU if ICE will be used to guide the implant procedure. *

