7.2 Methods for Handling Missing Data

All subjects who are enrolled will be eligible for evaluation, regardless of the treatment that ensues. Handling of dropouts and missing data will depend on their frequency and the nature of the outcome measure. Adjustments for missing outcomes data will be performed if deemed necessary to eliminate or minimize bias and will be described completely. Statistical models that account for censored data will be employed in appropriate circumstances, e.g., for time-to-event outcomes. Outlier values will be evaluated, and values determined to be invalid will be queried. All data will be included in the analysis unless judged to be invalid.

When calculating rates of adverse events for specific time intervals, missing and partial dates will be handled as shown below:

Partial Date Description	Action Taken
Entire onset date is missing	The implant procedure date will be used for

	the onset date.
The month and the day of the month are missing but the year is available	January 1 st will be used for the month and day of the onset date. However, if the imputed date falls before the implant procedure date, then the implant procedure date will be used for the onset date.
Day is missing, but the month and year are available	The 1 st will be used as the day of the onset date. However, if the imputed date falls before the implant procedure date, then the implant procedure date will be used for the onset date.

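### SAP 7.6 imputes medication start dates without asking whether the drug was taken before implant or had already been stopped, so some drugs are tabulated on the wrong side of implant

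*SAP*

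**What the plan says.** SAP 7.6 gives three rules for incomplete medication start dates.

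- Wholly missing: "The procedure date will be used for the start date".
- Day missing: "The 1 st will be used as the start day".
- Month and day missing: "January 1 st will be used for the month and day for start date".

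None of these rows refers to a medication review or to a stop date. The rows for partial stop dates do carry a check: "However, if the imputed stop date falls before the start date, then the start date will be used for the stop date". It moves an imputed stop forward to the start. It does nothing about an imputed start that falls after a known stop.

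The same section then sorts drugs into time windows. The first is "Prior to implant: medication started prior to implant". The second, *Post-implant*, covers "medication started and not stopped prior to implant OR medication started within 7 days post-implant".

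For adverse-event onset, SAP 7.2 bounds partial dates at implant: "However, if the imputed date falls before the implant procedure date, then the implant procedure date will be used for the onset date".

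The information needed to place a drug is already planned. Protocol 10.4 lists at baseline "Current medication regimen review for the use of antiplatelet, aspirin, and anticoagulant medications". Protocol 10.5 asks for pre-procedure medications to be recorded on the case report form. Table 10-1 requires a medication review at the index procedure and at each follow-up visit.

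**The concern.** The *Prior to implant* window depends on the start date alone, so any rule that moves a start date across the implant date changes the category. The rules can do this in both directions. The procedure-date default pulls a drug taken before implant forward to day 0. The first-of-month and 1 January defaults push a drug begun after implant back to before it.

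Antithrombotic treatment is reviewed at every visit, and the split at implant is what these windows exist to describe. At stake is whether the tables of drugs taken before and after implant are correct for records with incomplete start dates.

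**Working it through.** The plan gives no figure of its own to reproduce. The check applies the SAP 7.6 rules literally to test records and then counts how often the implant date is crossed.

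**Step 1: test records, implant on 20 March.**

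| Record | Imputed start | True windows | Windows after imputation |
|---|---|---|---|
| Long-term drug, ongoing, no start date | 20 March | Prior and Post-implant | Post-implant only |
| Long-term drug, stopped 10 March, no start date | 20 March | Prior only | Post-implant only |
| Started 21 March, day missing | 1 March | Post-implant | Prior and Post-implant |
| Started 4 May, day missing | 1 May | 45-day and later windows | unchanged |

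In the second row the imputed start is 10 days after the known stop. The drug still counts as *Post-implant*, because the second limb of that definition asks only for a start within 7 days and sets no condition on the stop.

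**Step 2: day missing, drug started k days after implant.** Take a 30-day month with the implant day d equally likely to be 1 to 30 (assumption). The imputed 1st precedes implant if d is at least 2. The start lies in the implant month if d is at most 30 − k. That leaves 29 − k of 30 days.

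- k = 1: 28/30 = 93%
- k = 7: 22/30 = 73%
- k = 29 or more: 0%

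Counting every implant date in the 2023 and 2024 calendars instead gives 97% at day 0, 93% at day 1, 90% at day 2, 74% at day 7, 51% at day 14 and 0% at day 30.

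**Step 3: only the year known.** The imputed date is 1 January. In a 365-day year with even implant dates, the start is moved to before implant in 364 − k of 365 cases.

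- k = 0: 364/365 = 99.7%
- k = 45: 319/365 = 87%
- k = 90: 274/365 = 75%
- k = 180: 184/365 = 50%

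The calendar count agrees.

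**Step 4: would the SAP 7.2 bound repair it?** With an implant-date floor on partial start dates, the drug started on 21 March is set to 20 March and is correctly *Post-implant* only. But a drug truly started on 5 March, with the day missing, is also set to 20 March and loses *Prior to implant*. The floor does nothing for a wholly missing start date.

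**The case against.** The strongest reply is that this is a small gap in a descriptive section, and that it is easy to claim too much from it. Several broader readings should be set aside.

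- A reader might infer that every long-term drug without a start date becomes a false post-implant count. It does not. An ongoing drug belongs in *Post-implant* anyway, through the limb for drugs started and not stopped before implant. Its error is the loss from *Prior to implant*. Full reversal needs a missing start and a stop before implant.
- A reader might infer that any post-implant drug with a missing day becomes a baseline drug. That needs a start in the implant month and an implant not on the 1st.
- The absence of an implant-date floor is not itself the defect. Adverse events are reportable from the index procedure (Protocol 17.1), so a floor suits them; medications legitimately start earlier.
- A reader might take baseline antiplatelet use to be inflated. The documents do not establish this. Protocol 10.5 recommends single antiplatelet therapy before implantation with a loading dose the day before, so for such drugs the 1st of the month usually gives the right category.
- Suitability for anticoagulation in the indication is a physician's judgement, and current use does not measure it. SAP 5.4 names no medication covariate, so an effect on those models is only conditional.
- An assumed 5% to 15% of 500 subjects with incomplete dates would be 25 to 75, but that counts incomplete dates and not misclassified subjects.

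It can also be said that sites must resolve data queries (Protocol 12.1), and that the form, which is not in the documents, may prevent missing dates. That may make incomplete dates rarer. It does not alter what the rule does to those that remain, and no other part of the SAP corrects it.

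**Conclusion.** The point holds in a limited form, and it is minor. On the literal text of SAP 7.6, every drug taken before implant with a wholly missing start date is lost from *Prior to implant*, and one stopped before implant is tabulated only as *Post-implant*. A day-missing start after implant but in the implant month is wrongly added to *Prior to implant* for about 93% of implant dates at day 1 and 73–74% at day 7, falling to zero by about day 30. With only the year known, the same can happen to any later start in the implant year.

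The percentages assume implant dates spread evenly over the month or year. They are shares of records with that kind of incomplete date, not of subjects. How many subjects are involved cannot be computed from the documents. The effect is on descriptive medication tables; no primary endpoint, hypothesis test or sample size changes.

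**What to change.** Amend SAP 7.6 so that the recorded baseline, pre-procedure and follow-up medication reviews decide the side of implant:

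1. If the drug is recorded as taken before implant, including pre-procedure medications such as a loading dose, an imputed start must fall before the procedure date.
2. If it is recorded as first taken at or after implant, an imputed start must not be earlier than the procedure date.
3. An imputed start must never fall after a known stop date.

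The test in rules 1 and 2 should be whether the drug was taken before implant, not when the form was completed, because Table 10-1 allows some baseline assessments to be collected after treatment. Do not apply a blanket floor at the implant date: it would misplace drugs truly started earlier in the implant month.

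The cost is SAP wording and a few lines of programming. No new data are needed.
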